### **12.4 Replacement of Subjects**

Subjects who withdraw from the study before Visit 5.2 will be replaced.

## **13 PROTOCOL VIOLATIONS**

A protocol violation occurs when the subject, investigator, or Sponsor fails to adhere to significant protocol requirements affecting the inclusion, exclusion, subject safety and primary endpoint criteria. Protocol violations for this study include, but are not limited to, the following:

- Failure to meet inclusion/exclusion criteria
- Use of a prohibited treatment/intervention

Failure to comply with Good Clinical Practice (GCP) guidelines will also result in a protocol violation. The Sponsor will determine if a protocol violation will result in withdrawal of a subject.

When a protocol violation occurs, it will be discussed with the investigator and a Protocol Violation Form detailing the violation will be generated. This form will be signed by a Sponsor representative and the Investigator. A copy of the form will be filed in the site's regulatory binder and in the Sponsor's files.

## 14 DATA SAFETY MONITORING

A data and safety monitoring plan (DSMP) will be used to monitor good clinical research procedures regarding data and safety of participants. During data collection, the Principal Investigator ([name]), and key personnel will monitor the practical aspects of the project to ensure that participants and the data are being protected, especially in conducting quality assurance of all informed consent documents in real time. All standard safety procedures and ethical practices will be adhered to per the IRB of the University of California, Los Angeles (UCLA) (a.k.a., Office of the Human Research Protection Program (OHRPP)), and will use secure, HIPAA-compliant technology per UCLA Health Sciences information and technology (DGIT) standards. [name] and key personnel will communicate regularly with UCLA OHRPP for coordinated review of ethical practices, safety procedures, and adherence to confidentiality/privacy agreements.

[name] will prepare administrative reports every month or more frequently as requested describing study progress including the following to review with primary mentor, [name], and co-mentor [name]:

- Actual versus expected enrollment figures
- Demographic and clinical characteristics
- Missing visits and case report forms
- Number and type of clinically significant/adverse events (CSEs), AEs and UPs
- Randomly audited consent forms of five participants to determine whether they are available and properly executed.
- Aggregate values of clinical laboratory results

## 15 STATISTICAL METHODS AND CONSIDERATIONS

Prior to the analysis of the final study data, a detailed Statistical Analysis Plan (SAP) will be written describing all analyses that will be performed. The SAP will contain any modifications to the analysis plan described below.

### 15.1 Data Sets Analyzed

All eligible patients who are enrolled into the study and attend the first study visit (the Safety Population) will be included in the safety analysis.

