
SUBJECT SELECTION CRITERIA
	
Inclusion Criteria
 
HIV-positive MSM with MUD in the contingency management condition (N = 35)
 
 
1. Assigned male sex at birth
 
2. 18 to 45 years of age
 
3. Reports having sex with men in the past 12 months.
 
4. HIV-positive (confirmed by certification or by HIV rapid test)
 
5. Has an HIV care provider (last seen in the past 12 months)
 
6. Has a current antiretroviral prescription
 
7. Meets the DSM-5 criteria for MUD using SCID-5
 
8. Urine test is positive for MA within 30 days of their screening visit
 
9. Seeking treatment for MUD.
 
10. Ability to attend twice weekly appointments for drug testing and treatment
 
 
HIV-positive MSM non-substance-using control (N = 20)
 
 
1. Assigned male sex at birth
 
2. 18 to 45 years of age
 
3. Reports having sex with men in the past 12 months.
 
4. HIV-positive (confirmed by certification or by HIV rapid test)
 
5. Has an HIV care provider (last seen in the past 12 months)
 

	
6. Has a current antiretroviral prescription
 
Exclusion Criteria
 
HIV-positive MSM with MUD in the contingency management condition (N = 35)
 
 
1. Identifies as (cis- or transgender) female
 
2. Reports another current or past substance use disorder
 
3. Reports being in another intervention or clinical trial for substance use
 
4. Positive test for opioids, cocaine, and/or MDMA
 
 
HIV-positive MSM non-substance-using control (N = 20)
 
 
1. Identifies as (cis- or transgender) female
 
2. Positive test for MA, opioids, cocaine, and/or MDMA.
 
3. Reports substance use (MA, opioids, cocaine, MDMA, hallucinogens, heavy alcohol use, and/or tobacco) in the past 6 months
 
4. Reports past or current substance use disorder
 

BEHAVIORAL INTERVENTION	
Those with MUD (MA+/HIV+) will receive contingency management, a positive reinforcement behavioral treatment with escalating rewards for consecutive negative urine tests, capped at a maximum of \$30 per negative result.

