### 4 STUDY DESIGN

#### 4.1 Study Overview

The proposed study will be a two-arm clinical trial design of 55 MSM living with HIV, of whom 35 HIV-positive MSM with MUD (MA+/HIV+) will receive contingency management for MA reduction, and 20 HIV-positive, non-substance-using MSM (MA-/HIV+) will participate as a control. There is extensive evidence that CM has greater efficacy than a non-contingent condition in the treatment of MUD (41-44, 46-49, 88), so it may raise ethical concerns to withhold CM from people with MUD who are willing to receive treatment. For this reason, this study uses a control of non-substance using HIV-positive (MA-/HIV+) MSM rather than a non-contingent yoked control of HIV-positive MSM with MUD (89). The use of a non-substance-using HIV-positive control will provide a baseline level of CTRA among HIV-positive MSM who do not have MUD or use other substances, which can be compared against CTRA levels in those with MUD. Screening data will be reviewed to determine subject eligibility. Subjects who meet all inclusion criteria and none of the exclusion criteria will be entered into the study. The following treatment regimens will be used:

- Contingency management twice weekly for 8 weeks, with post-treatment follow-up at Week 12.

- Non-substance-using control will not receive a treatment, but will be evaluated at Baseline, Weeks 4, 8, and 12.

The total duration of subject participation will be 14 weeks. The total duration of the study is expected to be 4 years: 1 year of rolling subject recruitment, 1 year for final subject follow-up, 1 year of biospecimen processing, and 1 year of analysis.

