### 9.1.3 Adverse Events

Information regarding occurrence of adverse events will be captured throughout the study. Duration (start and stop dates), severity/grade, outcome, treatment and relation to study drug will be recorded on the case report form (CRF).

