### 11.2.1 Serious Adverse Experience Reporting

Study sites will document all SAEs that occur (whether or not related to study drug) per UCLA OHRPP Guidelines. The collection period for all SAEs will begin after informed consent is obtained and end after procedures for the final study visit have been completed.

In accordance with the standard operating procedures and policies of the local Institutional Review Board (IRB)/Independent Ethics Committee (IEC), the site investigator will report SAEs to the IRB/IEC.

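### The Safety Population is limited to eligible patients, so a participant enrolled in error and exposed to study procedures can be left out of the safety analysis

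*Combined protocol and SAP*

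**What the plan says.** Section 15.1 (Data Sets Analyzed) is one sentence and defines one set: "All eligible patients who are enrolled into the study and attend the first study visit (the Safety Population) will be included in the safety analysis". It has three conditions: eligible, enrolled, and present at the first study visit. The sentence does not say whether that visit is Screening (S), Baseline (B) or Visit 1.1.

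Section 4.1 states the entry rule: "Subjects who meet all inclusion criteria and none of the exclusion criteria will be entered into the study". Section 13 accepts that this rule can fail. Its list of protocol violations includes "Failure to meet inclusion/exclusion criteria", and on the consequence it says: "The Sponsor will determine if a protocol violation will result in withdrawal of a subject".

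Event collection is not tied to eligibility. Section 9.1.3 says "Information regarding occurrence of adverse events will be captured throughout the study", and section 11.2.1 says "The collection period for all SAEs will begin after informed consent is obtained and end after procedures for the final study visit have been completed".

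Section 15.5 plans a safety interim when a quarter of participants have completed Week 4. It names no analysis population.

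**The concern.** A safety summary should describe everyone exposed to the study, whether or not they should have been entered. Here the protocol foresees people who are enrolled but not eligible, allows some of them to continue, collects their events, and then uses a definition that leaves them out.

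The exposure is real though modest. From Baseline a participant gives urine, completes a survey and has about 50 mL of blood drawn (section 10.2). In the CM arm he attends twice weekly from Visit 1.1 (section 8.2). Section 5.3 also counts methamphetamine use and viral load as safety evaluations, so an omitted participant could take those data with him as well as his adverse events.

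At stake is the completeness of the safety report in a study of 55 people, where one omitted event can turn an observed rate into zero.

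**Working it through.** The plan states no figure on this point, so the check is mainly a comparison of the text.

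**Step 1: does *eligible* restrict the set?** Section 15.1 lists eligibility beside enrolment. If everyone enrolled were eligible, as section 4.1 intends, the word would add nothing. Section 13 shows that the plan expects exceptions, so the word has an effect in exactly those cases.

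**Step 2: can an ineligible participant be exposed?** Yes. Under section 13, withdrawal is the sponsor's decision and is not automatic. A person entered through a screening error can have the Baseline procedures and CM visits before the error is found, and may be kept on afterwards.

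**Step 3: does any other section restore him to the analysis?** None does. Sections 9.1.3 and 11.2.1 govern collection and section 14 governs monthly reports; none of them defines an analysis set. Section 15 promises a detailed SAP that may modify the plan, but these documents contain no revised safety set.

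**Step 4: is eligibility itself clear?** Not fully. For the CM group, exclusion 4 in the synopsis reads "Positive test for opioids, cocaine, and/or MDMA", while the same item in section 6.3 omits MDMA. With *eligible* in the definition, the place of an MDMA-positive CM participant in the safety set depends on which list is applied. The two lists must be reconciled in any case; that is a separate matter.

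**Step 5: scale.** Inputs from the documents: 35 CM participants and 55 in total. The number enrolled in error, k, is not given; I assume 1 to 3.

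- Share of the CM arm, k/35: 1/35 = 2.9%; 3/35 = 8.6%.
- Share of all participants, k/55: 1/55 = 1.8%; 3/55 = 5.5%.
- One-sided 95% upper bound with zero events, 1 − 0.05^(1/n): 8.2% at n = 35; 8.4% at n = 34; 8.9% at n = 32.

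The loss of precision is therefore small. The observed rate can move either way:

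- If the one participant left out had the only event, 1/35 = 2.9% becomes 0/34 = 0%.
- If three event-free participants are left out and three events remain, 3/35 = 8.6% becomes 3/32 = 9.4%.

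**The case against.** The best defence is that *eligible* means judged eligible at screening. Section 4.1 has screening data reviewed before entry, section 15.1 describes no retrospective removal, and section 13 speaks of withdrawal from the study, not from an analysis set. That reading is possible. But it makes the word redundant, and it does not settle the case of someone entered although his own screening record shows a criterion unmet. The defence shows that the wording may be loose drafting; it does not make the definition safe to apply.

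Four stronger readings are tempting, and the documents do not support them.

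- *That undisclosed drug use or disorders found later would remove participants.* The relevant exclusions in section 6.3 turn on what the participant reports. Someone who did not report the matter at screening arguably met no exclusion, so later discovery does not clearly make him ineligible. Screening error is the route that section 13 clearly supports.
- *That adverse-event rates would be biased downwards.* This needs the omitted participants to have more events than the rest. Nothing in the documents shows that, and the arithmetic above goes in both directions.
- *That the safety interim excludes ineligible participants.* Section 15.5 names no population. Carrying the section 15.1 set over to it is a natural inference, but it is not stated.
- *That participants are left unprotected.* Adverse events are probed at each visit (section 11.1), serious events are documented from consent and reported to the ethics board (section 11.2.1), and section 14 requires monthly counts by number and type. None of these carries an eligibility condition.

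**Conclusion.** The point holds as a defect in the definition of the safety set. Taken literally, section 15.1 leaves out of the safety analysis any participant who was enrolled in breach of the criteria, even if he was exposed and his events were recorded. The gap is in the analysis, not in data capture or oversight.

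Its size is limited: 2.9% of the CM arm per participant, on the planned 35. The number affected is an assumption and could be zero. The direction of any effect on event rates is not known. The conclusion rests on the plain wording of sections 15.1 and 13, and on no later SAP having changed the set. It is worth correcting because the correction is so simple and because, in a small study, a single omitted event would be visible in the result.

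**What to change.** In section 15.1, delete *eligible* and define the Safety Population as all consented, enrolled participants who undergo any study procedure at or after Baseline (urine test, survey, blood draw or CM visit), regardless of any later finding on eligibility. In section 15.5, name this set as the population for the safety interim.

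The trigger should be any procedure and not only a blood draw or CM visit. Section 10.2 lists the urine test and survey before the blood draw, and section 2.1 names risks for both, so a participant who leaves Baseline before the draw should still count. Anchoring the set at Baseline also removes the doubt over which visit is the first. Serious events between consent and Baseline remain collected under section 11.2.1 and can be listed separately.

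The cost is a sentence in each of two sections. No extra data are needed, and the models in sections 15.3, 15.4 and 15.6 do not change.

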### 15.2 Demographic and Baseline Characteristics

Sociodemographic and behavioral covariates will include age, race, education level, sexual orientation, employment, income, body mass index (BMI) which is a known risk factor for inflammatory gene expression and a standard biological covariate in social genomics analysis (11, 98-100), smoking history, heavy alcohol use history.

### 15.3 Analysis of Primary Endpoint

Using mixed effects linear regression and marginal plots, we will estimate, graph, and compare trajectories of CTRA gene expression between those with methamphetamine use disorder in the contingency management (MA+/HIV+) and non-substance-using control (MA-/HIV+) conditions.

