Primary Analysis Plan	Using a linear mixed effects regression, we will test whether a negative MA urine test is associated with reductions in CTRA contrast scores across four time points—Visits B, 4.2 (Week 4), 8.2 (Week 8), and 12.0 (Week 12 follow-up). We will use a time (days) by MA urine result interaction term to estimate difference in change in CTRA as a function of MA test result. Using a mixed effects logistic regression, we will test whether CTRA expression is associated with viral suppression (<200c/mL) across three time points— Visits B, 4.2 (Week 4), 8.2 (Week 8), and 12.0 (Week 12 follow-up). We will include a time (days) by CTRA expression interaction term to test this association longitudinally.
Rationale for Number of Subjects	Power analysis for this pilot study indicates that a minimum of 135 person-observations will be sufficient to test whether MA use or the psychosocial Short Inventory of Problems (SIP-R) are associated with CTRA expression, assuming a medium effect size of 0.15 and power level of .80. Additionally, a logistic model testing whether CTRA is associated with viral suppression would require a minimum of 154 person-observations, assuming a power level of .80, a CTRA standard deviation of 1.44, mean centering of CTRA, and an odds ratio of 1.5. When modeling viral load as a continuous outcome, 135 person-observations is the minimum to test whether CTRA is associated with viral load (c/mL), assuming a medium effect size of 0.15 and power level of .80. These analyses will include 55 participants over four measurements of CTRA, for a total of 220 person-observations (176 person-observations at 80% retention), which is sufficient for these thresholds.

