### 3 STUDY OBJECTIVES

#### 3.1 Primary Objective

To investigate whether changes in CTRA gene expression coincide with changes in MA use and viral load over the course of 12 weeks in HIV-positive MSM with and without MUD.

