#### 3.2 Secondary Objectives

- To investigate whether differences in seven psychosocial dimensions of drug addiction (Short Inventory of Problems Revised (SIP-R))—physical, social, intrapersonal, interpersonal, impulse control—are associated with differences in CTRA gene expression.
- To conduct an exploratory pilot investigation to determine the degree to which CTRA mediates the association between MA use and viral suppression.

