## **5 CRITERIA FOR EVALUATION**

### **5.1 Primary Efficacy Endpoint**

The primary efficacy endpoint is a gene expression pattern called the conserved transcriptional response to adversity (CTRA), measured using transcriptome profiling of leukocytes. We will test whether this gene expression pattern coincides with changes in MA use and psychosocial domains of addiction severity.

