### **5.2 Secondary Efficacy Endpoints**

We will conduct negative urine tests for MA as a measure of abstinence. HIV viral load from will be quantified from plasma.

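### Section 15.3 and the synopsis label different analyses as primary, and nothing requires one primary test to be fixed before the Week 4 look at the endpoints

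*Combined protocol and SAP*

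**What the plan says.** Two places carry a primary-analysis label.

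- Section 15.3 uses mixed effects linear regression to "compare trajectories of CTRA gene expression between those with methamphetamine use disorder in the contingency management" group and the non-substance-using controls. It has no term for urine result or viral load.
- The synopsis, under Primary Analysis Plan, does not contain that comparison. It gives a linear mixed model in which "we will test whether a negative MA urine test is associated with reductions in CTRA contrast scores across four time points", with a time-by-urine interaction. It then gives a logistic mixed model in which "we will test whether CTRA expression is associated with viral suppression (<200c/mL) across three time points", with a time-by-CTRA interaction. (That sentence goes on to list four visits; the miscount is a separate slip.)

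Section 15.6 repeats both synopsis models without a primary label. In the second, the outcome is viral suppression and CTRA is the predictor, although the synopsis and Section 5.2 list viral load as a secondary endpoint.

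The objectives and endpoint text do not settle the matter. Section 3.1 reads "To investigate whether changes in CTRA gene expression coincide with changes in MA use and viral load", in men with and without MUD. Section 5.1 says the primary endpoint will be tested for whether it "coincides with changes in MA use and psychosocial domains of addiction severity", leaving out viral load and adding a question that Section 3.2 makes secondary ("To investigate whether differences in seven psychosocial dimensions of drug addiction").

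Section 15 promises a SAP before the final data are analysed and allows it to change the plan. Section 15.5 schedules an analysis of primary and secondary endpoints once all participants have completed Week 4.

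**The concern.** The labelled analyses answer different questions. The Section 15.3 contrast asks whether CTRA follows a different course in treated men with MUD than in men who do not use substances. The arms are not randomised and differ by design: Section 6.3 excludes controls who report tobacco use in the past six months, but has no such exclusion for the MUD arm. The first synopsis model asks whether CTRA goes with urine result. The second asks whether viral suppression goes with CTRA. One can be positive while the others are null.

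The study is meant to judge whether CTRA can serve as a treatment endpoint beyond abstinence. If the primary test is settled only after some results are known, a reader of the report cannot tell a pre-specified finding from the most favourable of several.

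**Working it through.** **1. The candidates side by side**

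| Candidate | Where | Outcome | Term of interest | Called primary? | Covered by 15.7? |
|---|---|---|---|---|---|
| A | 15.3 | CTRA | arm trajectory | yes, in 15.3 | no |
| B1 | synopsis, 15.6 | CTRA | urine result; time × urine | synopsis only | yes |
| B2 | synopsis, 15.6 | viral suppression | CTRA; time × CTRA | synopsis only | yes |

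B1 and B2 each contain a main effect and a time interaction. Choosing a model therefore still leaves open which coefficient is the test.

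**2. The plan's sample-size figures (Section 15.7)**

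- Observations: 55 × 4 = 220, and 220 × 0.8 = 176. Both reproduce.
- 135 for the linear models: reading 0.15 as f² with an assumed alpha of 0.05 and power 0.80, a 14-predictor omnibus F test gives exactly 135, while a one-degree-of-freedom test gives 55. The number of predictors is not stated.
- 154 for the logistic model: n = (1.96 + 0.84)² / [p(1 − p)(ln 1.5 × 1.44)²] gives 93 at p = 0.5, 144 at p = 0.80 and 153 at p = 0.815. The suppression rate p is not stated.

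The stated inputs do not fix 135 or 154, and neither is shown to be wrong. What matters here is their scope: each concerns an association with CTRA (MA use, psychosocial score, viral suppression or viral load). None concerns the arm-by-time contrast in Section 15.3.

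**3. Cost of leaving the choice open**

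The documents state no alpha, so I assume two-sided 5% per test and all nulls true.

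- Independent tests: 1 − 0.95³ = 0.143.
- Equally correlated normal test statistics: about 14% at correlation 0.3, 12.5% at 0.5 and 9.8% at 0.8.

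The risk therefore runs from about 10% (correlation 0.8) to about 14% (correlation 0), against 5% for one named test. The tests share participants and CTRA data, so some correlation is likely. The documents give no value for it.

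**4. Does the planned SAP close the gap?**

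It must precede analysis of the final data. The Section 15.5 analysis comes earlier, covers primary and secondary endpoints, and uses the models already described, which within Section 15 means 15.3 and 15.4. Nothing requires the SAP to be fixed before that look, and no masking is described.

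**The case against.** The best defence is that Section 15 has a readable order: 15.3 and 15.4 compare each endpoint by arm, and 15.6 studies associations between endpoints. On that reading CTRA is the primary endpoint throughout, and the only fault is the heading in the synopsis. A SAP is promised, and the study calls itself a pilot, so familywise error matters less than in a confirmatory trial. Most of this is fair, and it lowers the severity. It does not remove the conflict: two labels disagree, and the sample size follows the synopsis rather than 15.3.

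A reader might also infer four stronger points that the documents do not support.

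- *The Section 15.3 contrast does not test the primary objective.* The objective covers men with and without MUD, and Section 4.1 gives the controls the role of a CTRA reference level. The contrast addresses part of the objective, though not the link with MA use or viral load.
- *Section 5.1 creates a fourth primary analysis.* It is one sentence with no model, and Section 3.2 places the psychosocial question as secondary. This is a lesser wording conflict.
- *The choice is between a within-person and a between-arm analysis.* The urine term is not split into within- and between-person parts. Controls must test MA-negative at entry and Section 15.7 counts all 55 participants, so the coefficient mixes both.
- *The arm contrast is underpowered.* A simple mean comparison at one visit detects 2.80 × √(1/35 + 1/20) = 0.79 SD, or 2.80 × √(1/28 + 1/16) = 0.88 SD at 80% retention. Those are differences in level. A trajectory contrast needs its own calculation, and the documents supply no inputs for one.

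**Conclusion.** The point holds as a conflict of labels: Section 15.3 and the synopsis name different primary analyses, no single coefficient or alpha is given, and the planned SAP is only a partial safeguard because it may change the plan and may follow the Week 4 analysis. The consequence is a false-positive risk of about 10% to 14% rather than 5%. That range rests on three candidate tests, an assumed 5% alpha for each, all nulls true, and correlations between tests from 0.8 down to 0. It describes what the plan permits and is no evidence that anyone intends to select a result. Given the pilot status and the promised SAP, this should be fixed, but it is not a fatal flaw.

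**What to change.** Before the Week 4 analysis in Section 15.5:

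1. Name one primary model, one coefficient (main effect or time interaction) and one alpha, in the same words in the synopsis, 3.1, 5.1, 15.3 and 15.7.
2. Label every other analysis, including those in 15.6, secondary or exploratory. Remove the psychosocial domains from 5.1, or mark them secondary there to agree with 3.2.
3. State that the SAP's primary analysis is fixed before that look.

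The model of CTRA on urine result is the natural choice: it is in the synopsis, it addresses the MA-use part of 3.1, and 15.7 covers it. If it is chosen, 3.1 must also be edited so that viral load becomes secondary; otherwise a new mismatch appears. If the sponsor prefers to keep the arm contrast as primary, 15.7 needs a power statement for the trajectory contrast at the assumed 80% retention.

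The cost is protocol and SAP wording, plus one power calculation if the arm contrast stays. No visit, sample or data item changes.
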